## 2.8.3 Laboratory data

Central laboratory data will be summarized by presenting shift tables using extended normal ranges (baseline to most extreme post-baseline value), by presenting summary statistics of absolute data and change from baseline values (mean, medians, standard deviations, ranges) at each visit for which assessments are available for the parameters as in Table 2-4, and by the flagging of notable values in data listings by the criteria defined in Table 2-5. Listings will be provided for local laboratory evaluations for hematology and biochemistry parameters, as available.

Any values below the limit of quantification will be analysed as 0.5\* the lower limit. Any values above the limit of quantification will be analysed as 1.5\*the upper limit.

Liver safety analyses include frequencies of treatment-emergent elevations, a shift table of baseline and worst post-baseline values, respective narrow and broad "Possible drug related hepatic disorders - comprehensive search" SMQ and preferred term frequencies, eDISH plots, and narratives for any patients discontinued due to liver function abnormalities.

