**Table 2-5 Clinically notable laboratory values**

These laboratory abnormalities are based on a percent change from either Screening or Randomization:

Hematology	
RBC count	>50% increase, >20% decrease
Hemoglobin	>50% increase, >20% decrease
Hematocrit	>50% increase, >20% decrease
WBC count	>50% increase, >50% decrease
Platelet count	>75% increase, >50% decrease
Blood Chemistry	
ALT (SGPT)	>150% increase
AST (SGOT)	>150% increase
Alkaline phosphatase	>100% increase
Total bilirubin	>100% increase
BUN	>50% increase
Creatinine	>50% increase
Sodium	>5% decrease
Potassium	>20% increase, >20% decrease
Uric acid	>50% increase

To evaluate potential drug-induced liver injury, newly occurring liver enzyme abnormalities at any time post-baseline will also be summarized based on the event criteria in below table.

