**Table 2-6 Criteria for evaluating liver toxicity**

Parameter	Criteria
ALT	ALT > 3x ULN
	ALT > 5x ULN
	ALT > 8x ULN
	ALT > 10x ULN
	ALT > 20x ULN
AST	AST > 3x ULN
	AST > 5x ULN
	AST > 8x ULN
	AST > 10x ULN
	AST > 20x ULN
ALT or AST	ALT or AST > 3x ULN
	ALT or AST > 5x ULN

	ALT or AST > 8x ULN
	ALT or AST > 10x ULN
	ALT or AST > 20x ULN
ALT/AST & TBL	ALT or AST > 3x ULN & TBL > 1.5x ULN
	ALT or AST > 3x ULN & TBL > 2x ULN
	ALT or AST > 5x ULN & TBL > 2x ULN
	ALT or AST > 8x ULN & TBL > 2x ULN
	ALT or AST > 10x ULN & TBL > 2x ULN
	ALT or AST > 20x ULN & TBL > 2x ULN
ALP	ALP > 1.5x ULN
	ALP > 2x ULN
	ALP > 3x ULN
	ALP > 5x ULN
TBL	TBL > 1.5x ULN
	TBL > 2x ULN
	TBL > 3x ULN
ALP & TBL	ALP > 3x ULN & TBL > 2x ULN
	ALP > 5x ULN & TBL > 2x ULN
ALT/AST & TBL & ALP	ALT or AST > 3x ULN & TBL > 2x ULN & ALP ≤ 2x ULN (ALT or AST > 3x ULN & TBL > 2x ULN & ALP ≤ 2x ULN) or reported Hy's Law case
ALT or AST & AEs	ALT or AST > 3x ULN & (nausea or vomiting or fatigue or general malaise or abdominal pain or (rash and eosinophilia)

ULN: upper limit of normal

In addition, laboratory results meeting criteria (ALT/AST > 5x upper limit, Bilirubin > 2x upper limit, Creatinine > 265 umol, eGFR decrease ≥25%, 40% from baseline, potassium > 5.5 but <6.0 mmol/L or ≥6 mmol/L) specified in protocol appendix will be summarized.

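### If the central laboratory caps eGFR, the SAP's 1.5x upper-limit substitution adds spurious patients to the summarised eGFR-decrease criteria

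*SAP*

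**What the plan says.** SAP 2.8.3 has one substitution rule for all laboratory data. For low results: "Any values below the limit of quantification will be analysed as 0.5\* the lower limit". For high results: "Any values above the limit of quantification will be analysed as 1.5\*the upper limit".

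The same section then applies two sets of criteria that depend on percent change from baseline:

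- **Listing flags.** Notable values are shown "by the flagging of notable values in data listings by the criteria defined in Table 2-5". The table's introduction says: "These laboratory abnormalities are based on a percent change from either Screening or Randomization". The thresholds include more than 50% for BUN, creatinine and uric acid, more than 100% for total bilirubin ("Total bilirubin >100% increase") and alkaline phosphatase, and more than 150% for ALT and AST.
- **Summarised criteria.** The text after Table 2-6 adds a summary of results meeting criteria from the protocol appendix, including "eGFR decrease ≥25%, 40% from baseline".

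eGFR is in the list of analysed tests (SAP Table 2-4). Protocol 6.5.7.2 asks the laboratory to supply it, using the simplified MDRD formula. Neither document states a lower or upper reporting limit for any analyte, says whether eGFR is reported with a ceiling, or exempts substituted values from the percent-change criteria.

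**The concern.** A percent change calculated from a substituted value largely measures the substitution. The factors 0.5 and 1.5 produce steps as large as several of the thresholds, so a small true move across a reporting limit can count as a notable change.

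eGFR matters most. Its criteria are summarised, not only listed, and any ceiling used by the laboratory would pass straight into the rule because the laboratory supplies the value. Falls of 25% and 40% are also the surveillance and action levels in Protocol Appendix 5, and renal impairment is a named risk in Protocol 3.6. Spurious counts would arise in the patients with the highest eGFR. If they occur at similar rates in both arms, they can dilute a real difference in this row of the safety tables.

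**Working it through.** The plan gives no figure of its own to reproduce. Percent change is 100 × (follow-up − baseline) / baseline, with the SAP substitution put in. The limits L (lower) and U (upper) cancel, so the first two steps need no assay data.

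**1. Upper limit, falling (eGFR).** A baseline above U is analysed as 1.5U.

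| Follow-up | True change from 1.01U | Analysed change | ≥25% met | 40% met |
|---|---|---|---|---|
| 1.00U | −1.0% | 1.00/1.5 − 1 = −33.3% | yes | no |
| 0.99U | −2.0% | −34.0% | yes | no |
| 0.95U | −5.9% | −36.7% | yes | no |
| 0.90U | −10.9% | 0.90/1.5 − 1 = −40.0% | yes | yes |

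The 40% tier is read here as ≥40%. As an example with an assumed cap of 90, a baseline of 93 is reported as above 90 and analysed as 1.5 × 90 = 135.

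- Later value 89: true change 89/93 − 1 = −4%; analysed change 89/135 − 1 = −34%.
- Later value 80: true change 80/93 − 1 = −14%; analysed change 80/135 − 1 = −41%.

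**2. Lower limit, rising (listing flags).** A baseline below L is analysed as 0.5L.

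- Follow-up exactly L: L/0.5L − 1 = +100.0%. The >50% flags are met; the >100% flags are not, because the inequality is strict.
- Follow-up 1.01L: +102%, against a true change of about +2% from 0.99L. The >50% and >100% flags are both met.
- Follow-up above 1.25L: more than +150%, so the ALT and AST flags are met.

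**3. How often this could affect the eGFR summary.** This needs inputs that the documents do not give. The assumptions are: baseline eGFR N(62,20) truncated at 30, log-normal within-patient error, no treatment effect, and four post-baseline full central panels (Visits 102, 104, 199 and 299 in Protocol Table 6-1). The table shows the percentage of patients flagged at least once.

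| Assumption | No cap | Cap 90 | Cap 60 |
|---|---|---|---|
| CV 10%, ≥25% | 6.7 | 12.0 | 16.7 |
| CV 10%, 40% tier | 0.1 | 3.8 | 5.7 |
| CV 5%, ≥25% | 0.0 | 3.8 | 7.5 |

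At CV 10% the excess at ≥25% is 12.0 − 6.7 = 5.3 points with a cap of 90, and 16.7 − 6.7 = 10.0 points with a cap of 60. With a cap of 120 it is 0.5 points or less; with no cap it is zero. Changing only the baseline to N(55,15) lowers the cap-90 excess to 1.3 points and raises the cap-60 excess.

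**4. Substituting the limit itself.** The same crossings become 1.01L/L − 1 = +1% and 0.99U/U − 1 = −1%, and none of the criteria is met.

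**The case against.** The strongest objection is that the size rests on a fact absent from the documents. eGFR is a calculated quantity, the SAP speaks of a limit of quantification, and nothing says that the central laboratory reports eGFR with a ceiling. If it does not, the eGFR effect is nil. The baseline distribution and CV are also assumed, and the result moves with them. All of this stands, and it is why the size is given as a range starting at zero. It does not remove the defect: where a limit is crossed, the rule as written gives a wrong answer.

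The lower-limit part is weaker. Nothing shows that any patient starts below an assay's lower limit. Table 2-5 drives flags in listings only, and the summarised liver criteria use multiples of the upper limit of normal, not percent change. This also stands.

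A reader might go on to infer that the rule creates renal events or triggers clinical action. The documents do not support that. Renal events of special interest come from the CRF renal pages (SAP Table 2-3). Investigators act on local laboratory results (Protocol 6.5.7.2). Appendix 5 measures from Visit 1, while the SAP's general baseline is Visit 101 (SAP 2.1.1). Creatinine criteria also report renal deterioration without depending on an eGFR ceiling.

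Nor is it shown that a difference between arms is hidden. The rule is the same in both arms, the simulation compares no arms, and Protocol 9.5.2 plans no formal inference for safety. Dilution is possible, not demonstrated.

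**Conclusion.** The concern holds in a conditional form. The arithmetic is exact: a fall from above U to U or lower always meets the ≥25% eGFR criterion, and meets the 40% tier only at 0.90U or lower. A rise from below L to above L always exceeds the 50% and 100% flags. It would be too strong to say that the −33% step meets both eGFR tiers, or that +100% by itself meets the bilirubin flag.

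The consequence is spurious counts in one descriptive renal safety summary. Under the stated assumptions at CV 10%, they range from none to about 10 percentage points at ≥25%, depending on a reporting limit that must be obtained from the laboratory. The primary and secondary endpoints are not touched. The point merits a correction because the remedy is cheap and frees a summarised renal result from an unstated laboratory convention.

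**What to change.** Amend SAP 2.8.3 in two places:

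1. For the ≥25% and 40% decrease criteria, calculate eGFR in the analysis from central-laboratory serum creatinine by the simplified MDRD formula, the protocol's own formula.
2. For other analytes, set results outside the limit of quantification to the limit itself when a percent-change criterion is applied. Keep 0.5x and 1.5x for descriptive summaries only.

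Suggested text: *For percent-change and notable-value criteria, results outside the limit of quantification are set to that limit; the factors 0.5 and 1.5 apply to descriptive summaries only. For the eGFR decrease criteria, eGFR is derived from central serum creatinine using the simplified MDRD formula.*

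The cost is a short derivation. Central creatinine is scheduled from Visit 101 onwards (Protocol Table 6-1), and age, sex and race are collected (Protocol 6.2).

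The downside is that some true changes starting beyond a limit will be counted conservatively. This is why eGFR needs the first change as well as the second. With a cap of 60 and CV 10%, setting eGFR to the limit alone would flag about 2.1% at ≥25%, against about 6.6% with uncapped values in the same run. Deriving eGFR from creatinine avoids that undercount.

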**Table 2-4 List of laboratory tests**

Hematology	Biochemistry	Urine assessments
Hematocrit	Alanine amino-transferase (ALT)	Albumin
Hemoglobin	Albumin	Creatinine
Platelet Count	Alkaline phosphatase	Urine dipstick
Red Blood Cells count	Aspartate amino-transferase (AST)	
WBC Differential	Blood urea nitrogen (BUN) (OR urea ONLY for local laboratory unable to assess BUN)	
White Blood Cells count	Calcium	
	Chloride	
	Creatinine	
	eGFR	
	Fractionated bilirubin (if total bilirubin > 2x ULN)	
	Glucose	
	Lipid profile (total cholesterol, LDL, HDL, and triglycerides)	
	Potassium	
	Sodium	
	Total Bilirubin	
	Total protein	

	Uric Acid	
--	-----------	--

**Table 2-5 Clinically notable laboratory values**

These laboratory abnormalities are based on a percent change from either Screening or Randomization:

Hematology	
RBC count	>50% increase, >20% decrease
Hemoglobin	>50% increase, >20% decrease
Hematocrit	>50% increase, >20% decrease
WBC count	>50% increase, >50% decrease
Platelet count	>75% increase, >50% decrease
Blood Chemistry	
ALT (SGPT)	>150% increase
AST (SGOT)	>150% increase
Alkaline phosphatase	>100% increase
Total bilirubin	>100% increase
BUN	>50% increase
Creatinine	>50% increase
Sodium	>5% decrease
Potassium	>20% increase, >20% decrease
Uric acid	>50% increase

To evaluate potential drug-induced liver injury, newly occurring liver enzyme abnormalities at any time post-baseline will also be summarized based on the event criteria in below table.

**Table 2-6 Criteria for evaluating liver toxicity**

Parameter	Criteria
ALT	ALT > 3x ULN
	ALT > 5x ULN
	ALT > 8x ULN
	ALT > 10x ULN
	ALT > 20x ULN
AST	AST > 3x ULN
	AST > 5x ULN
	AST > 8x ULN
	AST > 10x ULN
	AST > 20x ULN
ALT or AST	ALT or AST > 3x ULN
	ALT or AST > 5x ULN

	ALT or AST > 8x ULN
	ALT or AST > 10x ULN
	ALT or AST > 20x ULN
ALT/AST & TBL	ALT or AST > 3x ULN & TBL > 1.5x ULN
	ALT or AST > 3x ULN & TBL > 2x ULN
	ALT or AST > 5x ULN & TBL > 2x ULN
	ALT or AST > 8x ULN & TBL > 2x ULN
	ALT or AST > 10x ULN & TBL > 2x ULN
	ALT or AST > 20x ULN & TBL > 2x ULN
ALP	ALP > 1.5x ULN
	ALP > 2x ULN
	ALP > 3x ULN
	ALP > 5x ULN
TBL	TBL > 1.5x ULN
	TBL > 2x ULN
	TBL > 3x ULN
ALP & TBL	ALP > 3x ULN & TBL > 2x ULN
	ALP > 5x ULN & TBL > 2x ULN
ALT/AST & TBL & ALP	ALT or AST > 3x ULN & TBL > 2x ULN & ALP ≤ 2x ULN (ALT or AST > 3x ULN & TBL > 2x ULN & ALP ≤ 2x ULN) or reported Hy's Law case
ALT or AST & AEs	ALT or AST > 3x ULN & (nausea or vomiting or fatigue or general malaise or abdominal pain or (rash and eosinophilia)

ULN: upper limit of normal

In addition, laboratory results meeting criteria (ALT/AST > 5x upper limit, Bilirubin > 2x upper limit, Creatinine > 265 umol, eGFR decrease ≥25%, 40% from baseline, potassium > 5.5 but <6.0 mmol/L or ≥6 mmol/L) specified in protocol appendix will be summarized.

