6.5.7 Laboratory evaluations

Laboratory samples will be analyzed at the central and local laboratories. Local laboratory results will allow investigators to proceed with study visit procedures without the need to wait for central laboratory results, which may take several days to arrive.

Central and local laboratory results need not agree in order for the investigator to qualify a patient for the trial or make a dose titration decision. Local laboratory assessments will be done *in addition to* central laboratory assessments, not instead of them.

It is the responsibility of the investigator to review all laboratory results and make an assessment of whether an abnormal or notable value is clinically significant, whether additional evaluations should be performed as judged appropriate, and whether the patient may continue in the trial. Sample collection should be conducted according to the standards and requirements of the local laboratory.

• Laboratory values that exceed the boundaries of a *notable laboratory abnormality of interest* (refer to Appendix 1) must be commented on by the investigator and additional laboratory evaluations should be performed, as judged appropriate by the investigator.

- If the laboratory abnormality induces clinical signs or symptoms, or requires therapeutic intervention, and satisfies the criteria defined in Section 7.1, then the diagnosis or medical condition must be entered on the AEs page of the patient's eCRF and any treatment necessary should be documented. If the laboratory abnormality is the primary reason for an unforeseen *prolongation* of hospitalization, or unforeseen hospitalization during the out-patient period, or otherwise fulfills the seriousness category of an AE, then the procedure for rapid notification of SAEs must be followed.
- Likewise, if the laboratory abnormality leads to LCZ696 dose changes or discontinuation of LCZ696, the patient must be followed until the abnormality resolves or until it is judged to be permanent. Any dose changes must be recorded in the DAR eCRF page. This investigation may include continued monitoring by repeat laboratory testing or by performing additional laboratory tests as deemed necessary by the investigator or the Sponsor's medical monitor.

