If patients experience clinically significant decrease in renal function, adjustment of concomitant medications, temporary down-titration or discontinuation of LCZ696 is recommended.

In elderly patients, volume-depleted patients (including those on diuretic therapy), or patients with compromised renal function, concomitant use of LCZ696 and NSAIDs may lead to an increased risk of worsening of renal function.

The use of LCZ696 in end-stage renal disease patients is not recommended and LCZ696 should be immediately discontinued if patient develops this condition during the study.

If a clinically significant renal event is reported during the study, the investigator must ensure completion of the CRF pages for 'Renal events reporting'.

Two types of response to serum creatinine increase are described:

Surveillance situation

If, at any time after enrollment, eGFR decreases by \geq 25% from baseline (Visit 1) (or if serum creatinine concentration increases to 2.5 mg/dL [221 μ mol/L]), the investigator will check for potentially reversible causes of renal dysfunction such as:

- Non-steroidal anti-inflammatory drug intake, antibiotics, or other treatments known to affect serum creatinine levels
- Volume decrease, including that resulting from excessive dosing of diuretics
- Urinary infection
- Urinary tract obstruction
- Study medication

Action situation

If a patient eGFR decreases by $\geq 40\%$ from baseline (Visit 1) (or if serum creatinine concentration rises above 3 mg/dL (265 μ mol/L), the investigator will check for potentially reversible causes of renal dysfunction (see above).

If the investigator judges that study medication has to be stopped, he/she should do so and also notify the Sponsor's Medical Monitor or his/her designee.

Thereafter, serum creatinine assessments will have to be **repeated at least each week** until levels return to acceptable values. If able to resume study drug treatment, renal function must be periodically monitored to ensure stability of eGFR.

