### 2.1.1 General definitions

In this study, patients are randomized to two Treatment groups:

- Pre-discharge initiation of LCZ696 treatment
- Post-discharge initiation of LCZ696 treatment

Thus *study treatment* in this document will refer to Pre-discharge and Post-discharge. *Study drug* will refer to LCZ696 film-coated tablets at doses of 50 mg, 100 mg, and 200 mg. *Treatment actually received* will refer to the *actual* treatment group, rather than the *randomized* treatment group.

The terms *date of first administration of study drug/treatment* and *date of last administration of study drug/treatment* are the first and last reported dates of administration of LCZ696 reported in the Drug Administration Record page of the eCRF.

The term *Study Day* in this document relates to the Analysis Relative Day, Relative Start Day or Relative End Day as applicable. *Study Day* is defined relative to the analysis reference date, which is the date of randomization; it is the number of days from the reference date to the analysis date. For all dates on or after the analysis reference date, the study day is the difference to the analysis reference date plus one day (ie for date  $\geq$  reference date, study day = date - reference date + 1); for any dates prior to the analysis reference date, the study day is simply the difference to the reference date (ie for date  $<$  reference date, study day = date - reference date). Thus the Subject Reference Start Date is designated as Study Day 1, while the date directly prior to the reference date is defined as Study Day -1 (there is no Study Day 0).

The *baseline* value for any analysis variable in general is defined as the value measured at Visit 101 (Randomization) for all analyses except when a specific definition or reason is provided. For information which is not collected at Visit 101, e.g. physical exam, demography, medical history, local laboratory assessment, etc., the information collected at Visit 1 will be used for *baseline* evaluations.

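### SAP 2.8.3 cites the protocol appendix for its renal laboratory criteria, but omits the creatinine 221 µmol/L surveillance limb and by default measures eGFR falls from Visit 101, where Appendix 5 uses Visit 1

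*SAP*

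**What the plan says.** **SAP 2.8.3, sentence after Table 2-6.** The renal items are creatinine above 265 µmol/L and "eGFR decrease ≥25%, 40% from baseline". The sentence presents its list as criteria "specified in protocol appendix will be summarized". It names neither a baseline visit nor a laboratory source.

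**Protocol Appendix 5.** There are two either/or situations:
- Surveillance: an eGFR fall of at least "25% from baseline (Visit 1) (or if serum creatinine concentration increases to 2.5 mg/dL", which the appendix equates to 221 µmol/L.
- Action: an eGFR fall of at least 40% "from baseline (Visit 1) (or if serum creatinine concentration rises above 3 mg/dL", equated to 265 µmol/L.

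**SAP 2.1.1.** Baseline in general "is defined as the value measured at Visit 101 (Randomization) for all analyses", unless a specific definition or reason is given. Visit 1 is the fallback for information not collected at Visit 101, and local laboratory assessment is one of the examples. SAP 2.3 repeats the rule.

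**Sources of creatinine.** Protocol Table 6-1 schedules local creatinine at Visit 1, at Visit 101 and at the later numbered visits. Central biochemistry starts at Visit 101. The opening of SAP 2.8.3 summarises central data and gives local data in listings only.

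**SAP section 4**, the list of changes from the protocol, mentions neither difference.

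**The concern.** A summary that names the protocol appendix as its source should apply the appendix's criteria. Here one of the four renal limbs is absent, and the two eGFR limbs appear to be measured from another visit. Investigators apply Appendix 5 during the trial, and Protocol 6.5.7.2 has them rely on local results. Local and central values may also differ, since "Central and local laboratory results need not agree in order for the investigator to qualify a patient for the trial".

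Patients enter after treatment for acute decompensation, so renal function may not be steady between Screening and Randomization. If it moves, the choice of reference visit changes who is flagged. At stake is whether the laboratory summary can be read as a count of patients who met the protocol's own renal criteria.

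**Working it through.** **1. Thresholds side by side**

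| Limb | Appendix 5 | SAP 2.8.3 |
|---|---|---|
| Surveillance, eGFR | fall ≥25% from Visit 1 | fall ≥25%, visit not named |
| Surveillance, creatinine | reaching 221 µmol/L | absent |
| Action, eGFR | fall ≥40% from Visit 1 | fall of 40%, visit not named |
| Action, creatinine | above 265 µmol/L | above 265 µmol/L |

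Unit check on the appendix's own pairs: 221/2.5 = 88.4 and 265/3 = 88.3. The two conversions agree, so 221 µmol/L is a distinct threshold and not a misprint of 265.

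**2. Which baseline applies.** The SAP sentence gives no visit, so the general rule in SAP 2.1.1 governs unless an exception applies. The Visit 1 fallback is for information not collected at Visit 101. Table 6-1 schedules creatinine at Visit 101 both locally and centrally, so the fallback is not triggered. If the summary uses central data, no Visit 1 value exists.

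**3. Effect of the baseline.** Let d be the relative change in eGFR from Visit 1 to Visit 101. A fall of f from Visit 101 corresponds to a fall from Visit 1 of 1 − (1 − f)(1 + d). The documents give no value for d, so a range is assumed.

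| d | SAP 25% flag, as a fall from Visit 1 | SAP 40% flag, as a fall from Visit 1 |
|---|---|---|
| −20% | 1 − 0.75 × 0.80 = 40% | 1 − 0.60 × 0.80 = 52% |
| −10% | 1 − 0.75 × 0.90 = 32.5% | 1 − 0.60 × 0.90 = 46% |
| 0 | 25% | 40% |
| +10% | 1 − 0.75 × 1.10 = 17.5% | 1 − 0.60 × 1.10 = 34% |
| +20% | 1 − 0.75 × 1.20 = 10% | 1 − 0.60 × 1.20 = 28% |

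With d = −10%, falls from Visit 1 of 25% up to 32.5% meet the appendix limb but not the SAP flag. With d = +10%, falls of 17.5% up to 25% are flagged by the SAP but do not meet the appendix limb.

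Worked patients, eGFR 60 at Visit 1:
- Visit 101 at 54, later 44: 1 − 44/60 = 26.7% from Visit 1 (surveillance); 1 − 44/54 = 18.5% from Visit 101 (no flag).
- Visit 101 at 54, later 35: 41.7% from Visit 1 (action); 35.2% from Visit 101 (no 40% flag).
- Visit 101 at 66, later 38: 36.7% from Visit 1 (below the action limb); 42.4% from Visit 101 (40% flag).

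**4. Is the missing limb redundant?** The documents name the simplified MDRD formula but not its exponent. Assume eGFR is proportional to creatinine to the power −k, with k from 1.0 to 1.25. A 25% eGFR fall is then a creatinine ratio of (1/0.75)^(1/k), which is 1.333 at k = 1.0 and 1.259 at k = 1.25. Creatinine reaches 221 µmol/L before that point if it starts above 221/1.333 = 166 or 221/1.259 = 176 µmol/L respectively. For such patients the 221 limb adds something the 25% limb does not.

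Example: a rise from 180 to 221 µmol/L is a 22.8% increase. The eGFR fall is 1 − 180/221 = 18.6% at k = 1.0 and 1 − (180/221)^1.25 = 22.6% at k = 1.25. This meets the surveillance criterion but none of the SAP's renal thresholds, including the 50% creatinine rise in Table 2-5.

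**The case against.** **The baseline conflict is inferred.** SAP 2.1.1 allows a specific definition to override Visit 101, and the reference to the appendix could be said to import its Visit 1 definition. Local laboratory assessment is even named as a Visit 1 example, and Table 2-5 in the same section allows change from Screening or Randomization. This stands in part, because the SAP does not expressly say that these falls are measured from Visit 101. It is still the weaker reading: the fallback needs information not collected at Visit 101, and the Table 2-5 wording governs that table only. At best the text is ambiguous, and two programmers could produce different tables. The missing 221 µmol/L limb does not depend on this question.

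**Central-only data is also inferred.** The sentence names no laboratory, and a central series would be defensible, since Protocol 6.5.7.2 gives consistency between centers as its purpose. This stands. The source needs to be stated.

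**The SAP does not promise counts of surveillance and action events.** A reader might infer that it does, and so conclude that its counts are wrong. The documents do not support that. The SAP never uses those terms, lists single thresholds, and is visibly selective: it also leaves out the Appendix 3 potassium band above 5.4 up to 5.5 mmol/L. Yet it does not call the list a selection, so a reader could take it for the appendix criteria.

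**Other renal outputs exist.** Renal events of special interest come from the CRF renal pages (SAP Table 2-3). AEs leading to discontinuation or dose adjustment are summarised separately (SAP 2.8.1). A reader might infer that renal findings cannot be related to dose changes at all; these outputs show otherwise.

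**The effect may be small.** Screening is expected to last 1 to 3 days. Excluding eGFR below 30 at Randomization also limits how many patients start with creatinine high enough for the 221 µmol/L limb to matter. Both points stand.

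**Conclusion.** The point holds, as a minor one. SAP 2.8.3 cites the appendix but omits its 221 µmol/L surveillance limb, and under the SAP's default rule it measures eGFR falls from Visit 101 where Appendix 5 says Visit 1. The summary may therefore flag a different set of patients from those meeting Appendix 5.

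The reach is narrow. The missing limb affects surveillance only, and the baseline affects only the eGFR limbs. A reader might infer that the SAP will miss patients in the action tier because a threshold was dropped. It was not: both 40% and 265 µmol/L are listed, so any action-tier difference comes from the baseline of the eGFR limb.

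The number of patients affected cannot be computed from the documents. The ±10% and ±20% figures rest on an assumed change between visits, and at zero change the two baselines agree. The 166 to 176 µmol/L range rests on an assumed exponent. The output is descriptive, and no primary or secondary analysis depends on it. No view is taken here on which renal threshold is clinically right.

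**What to change.** In SAP 2.8.3:
- Add creatinine reaching 221 µmol/L, and name the baseline visit and laboratory source.
- Report the two Appendix 5 criteria as either/or items against Visit 1: a 25% eGFR fall or 221 µmol/L, and a 40% eGFR fall or above 265 µmol/L.
- Use local creatinine, which is already entered from Visit 1 onward. Where local eGFR is not in the database, derive it with the simplified MDRD formula named in Protocol 6.5.7.2.
- Keep the central-laboratory change from Visit 101 as a separately labelled summary.

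The cost is SAP wording, one derivation and one extra table, with no new data collection. The drawback is between-site variation in local assays, which is a reason to keep the central summary beside it.

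The cheaper alternative is to remove the reference to the appendix, state that Visit 101 is the baseline, and record the difference in SAP section 4. That makes the table accurate about itself but gives no count of the Appendix 5 criteria.
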